**Analysis will be done using local lab data ie, investigator reported.**

## **10.7 Analyses of Exploratory Endpoints**

### **10.7.1 Antibody Formation**

The incidence and percentage of subjects who develop anti-AMG 820 antibodies (binding and if positive, neutralizing) at any time will be tabulated by dose group, if tested and if data available.

## **10.8 Pharmacokinetic or Pharmacokinetic/Pharmacodynamic Endpoints**

The analysis of pharmacokinetic endpoints will include data from all subjects who have received at least 1 dose of the investigational product and have at least 1 pharmacokinetic sample collected.

The PK parameters for AMG 820 and pembrolizumab will be estimated using standard non-compartmental PK methods and summarized by dose groups using means, standard deviations, medians, minimums and maximums for intensive and peak/trough determinations. PK parameters for AMG 820 and pembrolizumab will include, but not be limited to, maximum observed concentration ( $C_{max}$ ) and minimum observed concentration ( $C_{min}$ ). In addition, area under the concentration-time curve (AUC) and, if feasible, half-life ( $t_{1/2}$ ) will be determined for AMG 820. Serum concentrations at each time point along with PK parameter values may be listed for each subject. Individual AMG 820 concentration/time profiles will be plotted by dose group. Summary statistics will be computed for each sampling time and parameter as appropriate. Analyses to explore relationship between exposure and safety and exposure and efficacy may also be performed. Analyses will be conducted by Amgen Clinical Pharmacology Modeling and Simulation (CPMS).

## **10.9 Biomarker Endpoints**

The exploratory biomarker analysis will be carried out by computation biology group and is beyond the scope of this document.

**10.10 Changes from Protocol-Specified Analyses**

Due to business reason data is not collected for RECIST 1.1 hence analysis of RECIST 1.1 is excluded during SAP amendment 1 dated 16 January 2019.

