Group 2 will consist of up to 29 subjects with advanced pancreatic cancer (only 10 enrolled initially in the first stage) who have not received prior treatment with a PD-1/PD-L1/CSF-1/CSF-1R inhibitor. In [2012, Brahmer et al](#) reported a pembrolizumab ORR of 0% (0 of 14 patients) for pancreatic cancer. It is anticipated that the combination treatment of AMG 820 and pembrolizumab will have an ORR of 20% or higher in pancreatic tumors; an ORR of 5% or less is considered to be insufficient anti-tumor activity to warrant future research. If none of the initial 10 subjects have an objective response then the recommendation is for enrollment to Group 2 be stopped for futility. If 4 or more of the 29 subjects have an objective response then the true ORR is determined to be >5%. This Simon Two-Stage design provides 80% power when the

true ORR is 20% while maintaining a 1-sided, 5% alpha error when the true ORR is 5% or lower.

Group 3 will consist of up to 55 subjects (only 19 enrolled initially in the first stage) with NSCLC who have not received prior treatment with a PD-1/PD-L1/CSF-1/CSF-1R inhibitor, and who have tumor PD-L1 expression <50%. [Garon et al in 2015](#) reported a pembrolizumab ORR per RECIST1.1 of 13.1% (28 of 214 patients) for NSCLC patients with tumor PD-L1 expression <50%, and an ORR of 14.4% (21 of 146 patients) for those with tumor PD-L1 expression from 1% to 49%. It is anticipated that the combination treatment of AMG 820 and pembrolizumab will have an ORR of 30% or higher in low PD-L1 expressing subjects; an ORR of 15% or less is considered to be insufficient anti-tumor activity to warrant future research. If 3 or fewer of the initial 19 subjects have an objective response then enrollment to Group 3 will be stopped for futility. If 13 or more of the 55 subjects have an objective response then the true ORR is determined to be >15%. This Simon Two-Stage design provides 80% power when the true ORR is 30% while maintaining a 1-sided, 5% alpha error when the true ORR is 15% or lower.

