- Merging lesions:
 - When two or more index lesions merge, the smaller lesion should have 0 mm recorded for the current and all future assessments, and the larger lesion should have the longest diameter of the merged lesion recorded for the current assessment and be followed for future assessments.
- Separating lesions:
 - When an index lesion splits into 2 or more lesions, the largest measurable part of the split lesion should be considered to be the previously recorded index lesion with measurements provided for the current assessment and followed for future assessments. The remaining lesions would be non-index lesions. Any new lesions that result from separating should be documented as non-index lesions that were generated by separating and not truly new lesions.

- Index lesion response
 - Immune-related Complete Response (irCR) – complete disappearance of all index lesions in two consecutive observations at least 4 weeks apart
 - Pathologic lymph nodes must have reduction in short axis to < 10 mm
 - Immune-related Partial Response (irPR) – decrease of 30% or greater in tumor burden compared with baseline in two consecutive observations at least 4 weeks apart
 - Immune-related Stable Disease (irSD) - not meeting the criteria for irCR or irPR, in the absence of immune-related progressive disease
 - Immune-related Progressive Disease (irPD) – at least a 20% increase in tumor burden compared with nadir (at any single time point) in two consecutive observations at least 4 weeks apart
 - When the size of the tumor lesion is considered ‘too small to measure’ (eg, less than 5 mm), a default value of 5 mm should be assigned for index lesions. If this is nadir, irPD will be judged from the tumor burden calculated using the default value.
- Non-Index Lesion Response
 - irCR – complete disappearance of all non-index lesions.
 - Pathologic lymph nodes must have reduction in short axis to < 10 mm
 - irPR and irSD – non-Index lesions are not considered in the definition of irPR or irSD. Measurements of non-index lesions are not required, but they are evaluated at each timepoint as ‘present’, ‘absent’ or ‘unequivocal progression’. If a significant partial response is observed in a non-index lesion, it should be described as a comment.

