 - Subjects with a global deterioration of health status requiring discontinuation of treatment without radiographic confirmation of disease progression (confirmed irPD) at the time should have the reason for treatment discontinuation classified as 'clinical disease progression'. In this case, irPD cannot be assigned at the time as the overall objective tumor response. Every effort should be made to radiographically confirm irPD even after discontinuation of treatment.

Measurement and Tumor Response Assessment Based on modified irRECIST	
Measurable lesions	
 • ≥ 10 mm (unidirectional measure) • Pathologic lymph nodes: short axis ≥ 15 mm
Measurement of each lesion	The longest diameter (mm)
The sum of the measurements (SLD)	
 • The sum of the longest diameters (SLD) of all index lesions and new measurable lesions, if any • Up to 5 lesions per organ, up to 10 total
Response assessment	
 • irPD: $\geq 20\%$ increase from nadir and at least 5 mm absolute increase compared to nadir (requires confirmation) • irSD: $< 30\%$ decrease from baseline and $< 20\%$ increase from nadir • irPR: $\geq 30\%$ decrease from baseline (requires confirmation) • irCR: Disappearance of all lesions (requires confirmation)
New Lesions	The presence of new lesion(s) does not define progression. Measurable new lesions (≥ 10 mm): The measurements of the new lesions(s) are included in the SLD
Confirmation	Confirmation by 2 consecutive observations at least 4 weeks apart required for irCR, irPR and irPD.

Modified irRECIST Overall Response Assessment			
Measurable Response	Non-measurable Response		Overall Response
Index and new measurable lesions (tumor burden) ^a , %	Non-Index lesions	New non-measurable lesions	Using irRECIST
↓ 100%	Absent	Absent	irCR ^b
↓ 100%	Stable/NA	Any	irPR ^b
↓ 100%	Unequivocal progression	Any	irPR ^b
↓ $\geq 30\%$	Absent/Stable/NA	Any	irPR ^b
↓ $\geq 30\%$	Unequivocal progression	Any	irPR ^b
↓ $< 30\%$ to ↑ $< 20\%$	Absent/Stable/NA	Any	irSD
↓ $< 30\%$ to ↑ $< 20\%$	Unequivocal progression	Any	irSD
↑ $\geq 20\%$	Any	Any	irPD ^b
UE	Any	Any	UE
ND	Any	Any	UE
NA	Any	Any	UE

NA = not available; ND = not done; UE = unable to evaluate

^a Decrease assessed relative to baseline, including new measurable lesions (≥ 10 mm)

^b Response (irCR, irPR) and progression (irPD) are confirmed by a second, consecutive assessment at least 4 weeks apart.

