#### 4. Study Endpoints and Covariates

##### 4.1 Study Endpoints

###### Primary Endpoints:

- Dose limiting toxicities (DLT), treatment-emergent adverse events, treatment-related adverse events and clinically significant changes in vital signs, physical examinations, and clinical laboratory tests
- Objective response rate (ORR) per irRECIST in subjects treated at the recommended combination dose

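### Group 3 sets an irRECIST response rate against a RECIST 1.1 benchmark, and the SAP drops the planned RECIST 1.1 response rate without a substitute

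*SAP*

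**What the plan says.** The primary efficacy endpoint in SAP 4.1 is "Objective response rate (ORR) per irRECIST in subjects treated at the recommended combination dose". Protocol 10.3.1 and SAP 8.1 base the stage 2 recommendation on irRECIST as read at the site.

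For Group 3, Protocol 10.2 (repeated in SAP 3.2) says that the cited NSCLC study "reported a pembrolizumab ORR per RECIST1.1 of 13.1% (28 of 214 patients) for NSCLC" with PD-L1 expression below 50%. It then sets the null: "an ORR of 15% or less is considered to be insufficient anti-tumor activity". Enrolment stops at 3 or fewer responses in 19, and success is 13 or more in 55. The stated power is 80% at a true rate of 30%, with a one-sided 5% limit on the type I error.

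Protocol Appendix D defines the modified irRECIST. In its summary table, "The presence of new lesion(s) does not define progression". In its overall-response table, a fall in measurable burden of 30% or more is irPR even with unequivocal progression of non-index lesions or with any new non-measurable lesion.

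Protocol 10.1.1.2 and 10.4.3 planned response by RECIST 1.1 as a secondary endpoint, with 90% and 95% confidence intervals. SAP 10.10 removes it: "Due to business reason data is not collected for RECIST 1.1 hence analysis of RECIST 1.1 is excluded". SAP 5 keeps the hypothesis that AMG 820 improves on pembrolizumab alone.

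**The concern.** The rate observed in Group 3 and the rate behind its null come from different response criteria. The trial's criterion is the more permissive of the two on new lesions and non-index progression. Part of any excess over the benchmark could therefore reflect the criteria rather than AMG 820. The planned RECIST 1.1 rate would have let a reader judge how much, and the SAP puts nothing in its place.

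The point is specific to Group 3. Group 1's benchmark is quoted on both RECIST 1.1 and irRC, the criterion for Group 2's benchmark is not stated, and Group 4 has no numerical benchmark.

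**Working it through.** **Inputs.** From Protocol 10.2, Group 3: n1 = 19, stop at 3 or fewer; n = 55, success at 13 or more; null 15%; alternative 30%; benchmark 28/214 = 13.1% by RECIST 1.1. The benchmark study's PD-L1 1–49% subset gave 21/146 = 14.4%.

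**Formula.** For a true response rate p, taking the stage 1 stop as followed:

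P(success) = Σ over x = 4 to 19 of P(X1 = x | 19, p) × P(X2 ≥ 13 − x | 36, p), with both terms binomial.

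**The plan's own figures first.** At p = 0.15 the terms for x = 4, 5, 6, 7, 8, 9, 10, 11 are 0.01373, 0.01470, 0.01084, 0.00563, 0.00209, 0.00057, 0.00011 and 0.00002, and later terms are negligible. They add to 0.0477. At p = 0.30 the same sum is 0.8006. The stated 80% power reproduces and the stated 5% limit is met. The Simon arithmetic is not in error.

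**Margin between null and benchmark.** 15 − 13.1 = 1.9 percentage points.

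**Effect of a shift in criteria.** The documents give no conversion from RECIST 1.1 to irRECIST. The rates above 15% are assumptions, shown as a range for what pembrolizumab alone might give by irRECIST. The last column is p × 214 − 28, the extra responders that the benchmark study would have needed.

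| True rate p | P(success) | P(stage 2 opens) | Extra responders in 214 |
|---|---|---|---|
| 13.1% (benchmark) | 1.8% | 23.2% | 0 |
| 15% (null) | 4.8% | 31.6% | 4.1 |
| 16% (assumed) | 7.2% | 36.2% | 6.2 |
| 17% (assumed) | 10.5% | 40.9% | 8.4 |
| 18% (assumed) | 14.4% | 45.5% | 10.5 |

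Solving P(success) = 0.05 gives p = 0.151. That is 0.151 × 214 = 32.3 responders, about 4.3 more than 28, a relative rise of about 15%.

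**One subject.** A threshold of 12 in 55 would carry a type I error of 8.3% at p = 0.15, against 4.8% for 13. The 90% Clopper-Pearson interval is 14.6% to 34.9% at 13/55 and 13.1% to 32.9% at 12/55. A single subject who responds by irRECIST only can decide whether the success rule is met.

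**Can a RECIST-1.1-type rate be derived?** Appendix D requires index lesions to be recorded and measured, and new measurable lesions to be added to the burden. Of the rest it says "Measurements of non-index lesions are not required, but they are evaluated at each timepoint", with unequivocal progression as one of the categories. Its response table also uses new non-measurable lesions. These are the components needed. The case report form is not among the documents, so whether each item is held in the database cannot be confirmed.

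**The case against.** The strongest reply is that the net bias against 13.1% has no known sign. This trial requires confirmation at least 4 weeks later and uses investigator reads; the documents do not say whether the benchmark responses were confirmed or who read them. Protocol 2.1.5 reports somewhat lower rates in previously treated than in treatment-naive patients (15.6% against 19.2%, and 9.1% against 16.7%). Group 3 subjects must be refractory to standard treatment, intolerant of it or refusing it. New measurable lesions count in the tumour burden, which limits the leniency of irRECIST. The null already allows 1.9 points, and nothing in the documents shows a shift larger than that. The decision rule always used irRECIST, RECIST 1.1 was a descriptive secondary endpoint, and its removal is disclosed. The rationale for Amendment 2 records that the sponsor has decided to stop investigating the combination, so a false Group 3 success is unlikely to drive further development.

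All of this stands, and it limits the size of the point. It does not make the two criteria the same, and disclosure does not replace the analysis that was removed.

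A reader might go further in four ways that the documents do not support:

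- That the type I error is in fact inflated, or that a Group 3 success would be an artefact. This needs an irRECIST rate on pembrolizumab alone above about 15.1%, which is an assumption.
- That no new data are needed. Appendix D tells sites what to assess, but SAP 10.10 says that RECIST 1.1 data are not collected, and the form cannot be checked.
- That a derived rate would be a true like-for-like comparison. It would still use up to 10 index lesions, exclude fluid collections and rest on local reads.
- That every group needs the analysis. Only Group 3 has a benchmark stated on RECIST 1.1 alone.

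**Conclusion.** The concern holds as a matter of comparability, at moderate weight. Group 3's irRECIST rate will be read against a null 1.9 points above a RECIST 1.1 benchmark, and the SAP removes the one planned analysis on the benchmark's criterion. The rule's exact type I error is 4.8% at the 15% null, against a stated limit of 5%, and 1.8% at the benchmark itself. It exceeds 5% only above about 15.1%, reaching 7.2%, 10.5% and 14.4% at assumed rates of 16%, 17% and 18%. These figures treat the stage 1 stop as followed and the criteria shift as the only difference from the benchmark. The true shift is not in the documents, and the other differences could offset it or add to it.

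**What to change.** In SAP 10.6, add for Group 3 a supportive RECIST-1.1-type response rate beside the irRECIST rate, with 90% and 95% Clopper-Pearson intervals. Derive it from the index measurements, new-lesion records and non-index status required by Appendix D, provided these lesion-level items are in the database.

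Count an irRECIST responder as a non-responder if any of the following is present at or before the response scan, or at its confirmation scan:

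- a new lesion;
- unequivocal progression of non-index lesions;
- a rise of at least 20% and 5 mm from nadir.

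Read any comparison with 13.1% against this rate. In SAP 10.10, state that the irRECIST rate and the Group 3 benchmark use different criteria. If the lesion-level items prove not to be held, that statement is the minimum.

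The primary endpoint, decision rule and sample size do not change. The cost is a small amount of programming. The result is only an approximation to RECIST 1.1, because up to 10 index lesions are used and fluid collections are excluded. Because the rule only removes responders, the rate can only equal the irRECIST rate or fall below it.

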**11. List of Planned Tables, Figures and Listings [TFLs]**

The definitive list of TFLs to be produced for this study is documented in the PRISM.

**13. Data Not Covered by This Plan**

Exploratory data not included in this plan may be analyzed at a later date or may be analyzed by a different Amgen Department.

14. Appendices

## Appendix A. Code Fragments

Provisional Code Fragments for calculating a confidence interval using the Clopper Pearson Method. The following example SAS code will be utilized for the response rate analysis providing the proportion of subjects responding to treatment with corresponding 95% confidence intervals.

```
data propci (keep = ns p low_ci upp_ci);
n=xx; * total n within the treatment group;
ns= xx; *number of responders;
p=ns/n; * response rate;
q=1-p;
lowF=FINV(0.025, 2*ns, 2*(n-ns+1)); /* use for 2-sided 95% CI */
UppF=FINV(1-0.025, 2*(ns+1), 2*(n-ns)); /* use for 2-sided 95% CI */
low_ci = 1 / (1+(n-ns+1) / (ns*lowf)); * lower CI for response rate;
upp_ci = 1 / (1+(n-ns) / ((ns+1)*uppf)); *upper CI for response rate;
if p=1 then upp_ci=1;
if p=0 then low_ci =0;
output;
end;run;
```

For 90% confidence intervals.

```
data propci (keep = ns p low_ci upp_ci);
n=xx; * total n within the treatment group;
ns= xx; *number of responders;
p=ns/n; * response rate;
q=1-p;
lowF=FINV(0.05, 2*ns, 2*(n-ns+1)); /* use for 2-sided 90% CI */
UppF=FINV(1-0.05, 2*(ns+1), 2*(n-ns)); /* use for 2-sided 90% CI */
low_ci = 1 / (1+(n-ns+1) / (ns*lowf)); * lower CI for response rate;
upp_ci = 1 / (1+(n-ns) / ((ns+1)*uppf)); *upper CI for response rate;
if p=1 then upp_ci=1;
if p=0 then low_ci =0;
output;
end;run;
```
